4. OVERALL STUDY DESIGN

4.1. Study Design

This is a multicenter, open label study of Dara+Pom+Dex combined with ATRA in patients progressing on a Dara+Len+Dex regimen. The study is expected to enroll up-to a maximum of 42 patients (20-32 subjects previously exposed to Dara + Len + Dex; 10-22 subjects previously exposed to Dara + Pom + Dex)..

The phase 1b portion will follow a standard 3+3 dose escalation design with two dose levels and up to 12 patients. Under this design, the investigators will evaluate dose levels as follows:

- Dose level 1 - ATRA 35.5 mg/m²/day on days -2,-1 and 1 on a 28-day cycle in combination with daratumumab, pomalidomide, and dexamethasone
- Dose level 2 – ATRA 45 mg/m²/day on days -2,-1 and 1 on a 28-day cycle in combination with daratumumab, pomalidomide, and dexamethasone

During the dose-escalation phase and after the first cycle, and after the first cycle, patients who have not experienced a DLT, have not shown signs of PD, and in the opinion of the investigator would continue to benefit from treatment may receive additional cycles of treatment.

The phase 2 portion will be conducted in two stages. In the first stage, 10 patients will be accrued. A safety and efficacy analysis will be conducted 3 months after accrual of the first 10 patients. If there are 2 or fewer responses in these 10 patients, the study will be stopped due to futility. If the stopping rules for safety are met, then the study will be stopped due to toxicities. Otherwise, accrual will continue for a maximum of 42 in phase 1b and phase II combined.

During 28-day treatment cycles, patients will receive Dara 1800 mg subcutaneous (SC) at their current dose upon enrollment onto the study depending on their cycle. (If they are on cycles 1-2 then they will receive Dara 1800 mg SC days 1,8,15,22; if they are on cycles 3-6 they will receive Dara 1800 mg SC days 1 and 15; if they are on cycle 7 or beyond they will receive Dara 1800 mg SC on day 1).

Pomalidomide will be administered at the patient's currently tolerated dose (4,3, or 2 mg po daily) on days 1-21. For patients progressing on daratumumab, lenalidomide, and dexamethasone, the starting dose of pomalidomide will be 4 mg per standard of care.

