Hyperglycemia \geq Grade 3	Decrease dose by one dose level. Treat with insulin or oral hypoglycemic agents as needed.
Acute pancreatitis	Discontinue subject from Dex treatment regimen.
Other \geq Grade 3 Dex-related adverse Events	Stop Dex dosing until the adverse event resolves to \leq Grade 2. Decrease by one dose level when Dex dosing is resumed.

^a If recovery from toxicities is prolonged beyond 14 days, then the dose of Dex will be decreased by one dose level when dose is restarted.

Table 7: Dexamethasone Dose Reduction Steps

Dose Level	≤ 75 years old	>75 years old
Starting Dose	40 mg	20 mg
Dose Level -1	20 mg	12 mg
Dose Level -2	10 mg	8 mg

ATRA will be administered in a divided dose of twice daily as an oral formulation at 35 mg/m²/day for Phase with dose escalation to 45mg/m²/day for 3 days. The dose expansion phase will be at the 45 mg/m²/day dose after safety and efficacy has been evaluated. The first administration of ATRA will be given in the morning, two days before the scheduled Dara infusion. The last administration of ATRA will be given in the evening of the day that Dara was administered (days -2, -1, and 1; day 1 is the day of Dara infusion).

ATRA-related toxicities

Subjects will be monitored for neurological symptoms and nutritional status. If Wernicke's encephalopathy is suspected, ATRA should be interrupted and parenteral thiamine should be initiated.

Pseudotumor cerebri

This complication has been mainly reported in patients aged <20 years and is characterized by presence of severe headache with nausea, vomiting, and visual disorders.

It is recommended to temporarily discontinue ATRA treatment and to administer opiates. As soon as the symptoms and the patient clinical conditions improve, the treatment with ATRA will be resumed at 50% of the previous dose during the first 7 days after the amelioration of pseudotumor cerebri. Thereafter, in absence of worsening of the previous toxicity, ATRA should be resumed at full dosage.

Table 8: ATRA Dose Reduction Steps

Dose Level	ATRA Dose reduction
Dose Level 2	45 (mg/m ²)
Dose Level 1 (Phase 1b starting dose)	35.5 (mg/m ²)
Dose Level -1	25 (mg/m ²)
Dose Level -2	20 (mg/m ²)

- ATRA will be discontinued for any Grade 4 non-hematologic toxicity.
- In the case of Grade 3 toxicity, ATRA should be held until the toxicity resolves to Grade ≤ 1 or baseline, at which time it may be resumed at a reduced dose.

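### The half-dose restart of ATRA after pseudotumor cerebri runs on a 7-day clock that often contains no scheduled ATRA day, so the step can be skipped

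*Combined protocol and SAP*

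**What the plan says.** Section 7.5 (Dose Modification, ATRA-related toxicities) advises stopping ATRA temporarily for pseudotumor cerebri. The restart is triggered by recovery: "As soon as the symptoms and the patient clinical conditions improve", ATRA is to be "resumed at 50% of the previous dose during the first 7 days after the amelioration of pseudotumor cerebri". The next step reads: "Thereafter, in absence of worsening of the previous toxicity, ATRA should be resumed at full dosage".

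The schedule is set elsewhere. Section 4.1 gives the second dose level as "ATRA 45 mg/m²/day on days -2,-1 and 1 on a 28-day cycle", with the same days at 35.5 mg/m²/day. Table 1 marks ATRA only under Days -2, -1 and Day 1, in Cycle 1 and in later cycles. Section 7.5 ends each course on the daratumumab day: "The last administration of ATRA will be given in the evening of the day that Dara was administered".

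Two general rules follow Table 8 in Section 7.5. The rule for Grade 3 events is this: "ATRA should be held until the toxicity resolves to Grade ≤ 1 or baseline, at which time it may be resumed at a reduced dose". The rule for Grade 4 events is this: "ATRA will be discontinued for any Grade 4 non-hematologic toxicity". Section 7.6 adds rules for Cycle 1 dose-limiting toxicities judged dangerous to retreat, for life-threatening Grade 4 events, and for cycle delays of more than 21 days caused by ATRA toxicity.

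**The concern.** The restart rule counts calendar days from improvement. The drug is given in three-day blocks four weeks apart. Nothing ties the 7 days to a dosing day or to the next block. The wording would suit a drug taken daily, where 7 days after improvement means 7 half-dose days. On this schedule the window can open and close with no dose due.

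What is at stake is the protocol's own safeguard. It chose a graded return after a neurological toxicity: half dose first, then full dose if nothing worsens. If no half dose is given, the check for worsening is made while the patient is off the drug, and the first re-exposure is at full dose.

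**Working it through.** No power or sample-size formula applies; the check is a calendar count.

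**Inputs**
- ATRA days: -2, -1 and 1 of each cycle (Section 4.1, Table 1, Section 7.5).
- Cycle length: 28 days (Section 4.1).
- Half-dose window: 7 days after improvement (Section 7.5).
- Dose levels: 45 and 35.5 mg/m²/day (Section 4.1, Table 8).
- Visit window for the ATRA days and Day 1: plus or minus 10 days (Table 1).
- Pomalidomide: Days 1 to 21 (Section 4.1).

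**Next block, cycle on time.** The next Day 1 is Day 28 + 1 = 29 of the current cycle, so Days -2 and -1 are Days 27 and 28. The block is Days 27, 28 and 29.

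**Window.** For improvement on Day t, the window is Days t+1 to t+7. It misses the block when t + 7 < 27, that is, when t ≤ 19.

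| Improvement on | Scheduled ATRA days at half dose |
|---|---|
| Days 2–19 | 0 of 3 |
| Day 20 | 1 of 3 (Day 27) |
| Day 21 | 2 of 3 (Days 27, 28) |
| Days 22–26 | 3 of 3 |

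Improvement on Day 20 or 21 changes the dose inside one block. Day 1 is left out because that evening's ATRA dose could still be given at half.

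**Counting conventions.** If the day of improvement counts as the first of the 7, the window is t to t+6 and the empty range is Days 2 to 20. Days 2 to 19 are empty either way. The Protocol Summary and one paragraph of Section 4.1 call the daratumumab day Day 0. ATRA still starts two days before daratumumab, so this is a labelling difference. Even a literal Day 0 between Days -1 and 1 would move the cut-off by only one day.

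**Cycle not on time.** If the next cycle starts d days late (negative for early), the last empty day is 19 + d.
- Early: a next Day 1 on Day 22 is 7 days early, within the visit window and clear of pomalidomide Days 1 to 21. The block is Days 20 to 22, and the last empty day is 19 − 7 = 12.
- Late: the cut-off moves beyond Day 19, day for day.

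**Dose at first re-exposure when the window is empty**
- 45 mg/m²/day instead of 45 × 0.5 = 22.5. Over the block: 3 × 45 = 135 against 3 × 22.5 = 67.5 mg/m².
- 35.5 mg/m²/day instead of 35.5 × 0.5 = 17.75. Over the block: 3 × 35.5 = 106.5 against 3 × 17.75 = 53.25 mg/m².

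**Example.** A patient on 45 mg/m²/day improves on Day 10. The window is Days 11 to 17, and no ATRA is scheduled in it. The next dose is on Day 27, 27 − 10 = 17 days after improvement, at 45 mg/m²/day.

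These counts are calendar days, not probabilities. The documents give no distribution of time to improvement.

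**The case against.** **Other rules may already catch these patients.** Section 7.5 describes the complication as a severe headache with vomiting and visual disturbance, which suggests Grade 3 or above. The fallback scale in Section 10.3 equates severe with Grade 3, but only for events that CTCAE does not define, so this is not decisive. If the Grade 3 rule under Table 8 governs, ATRA is held and any restart is at a reduced dose, and the full-dose re-exposure does not arise. Grade 4 is covered by Table 8 and Section 7.6. This objection stands as a limit on scope. It does not remove the point: the documents do not say which rule prevails at Grade 3, and below Grade 3 the pseudotumor paragraph is the only specific restart rule.

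**The rule can be read as a cap.** On that reading, any ATRA given within 7 days of improvement is halved, and if none is due the cap does not bind. This is coherent, and the patient then restarts at least 8 days after improvement. But the graded step the paragraph describes is then not delivered.

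**A reader might infer that sites would dose at once,** giving 7 half-dose days off schedule. The opening words of the restart sentence lend this some support. However, Section 4.1, Table 1 and Section 7.5 confine ATRA to the three-day block, and nothing authorises other days. The point does not rest on this reading.

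**A reader might also infer that full-dose re-exposure after the gap is harmful.** No document shows that.

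**The event should be rare.** Section 7.5 says that it is reported mainly in patients under 20; the trial enrols adults, at most 42 of them. This stands, and it sets the severity.

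**Conclusion.** The point holds as a minor correction. With ATRA kept to its scheduled days and the next cycle on time, improvement on Days 2 to 19 leaves no half-dose day. The last empty day is Day 12 if the next Day 1 is brought forward to Day 22, and later than Day 19 if the cycle is delayed. In the empty range, first re-exposure is at twice the intended daily dose, with no on-drug check for worsening beforehand.

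The conclusion covers events below Grade 3. It covers Grade 3 events only if the pseudotumor paragraph overrides the rule under Table 8. The trial's test of overall response rate is unaffected.

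A reader might conclude that Grade 3 patients should stay at a reduced dose permanently. The documents do not settle that: the Table 8 rule permits a reduced dose on restart, while the pseudotumor paragraph returns patients to full dose.

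**What to change.** In Section 7.5, replace the 7-day clock with a step defined by treatment block:
- Give the first resumed scheduled three-day ATRA block at 50% of the previous dose.
- Give no ATRA on unscheduled days.
- Return to full dose at the next block only if the half-dose block was tolerated without worsening.
- State whether this paragraph or the Grade 3 rule under Table 8 governs Grade 3 events.

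The cost is one edited paragraph, with no extra procedures or patients. The downside for an affected patient is one block at half dose: 135 − 67.5 = 67.5 mg/m² less at 45 mg/m²/day, or 106.5 − 53.25 = 53.25 mg/m² less at 35.5.

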7.6. Criteria for Discontinuing ATRA and Discontinuation from Study

ATRA should be discontinued in patients experiencing an AE in Cycle 1 meeting criteria for a DLT for which the investigator considers that retreatment of the patient could be dangerous. For Grade 4 life threatening TEAEs, the subject will be permanently withdrawn from study, except when the investigator determines that the patient is receiving clinical benefit and there are chances to provide supportive care to mitigate the Grade 4 event to recur. In these circumstances, treatment may be restarted at the previously safe dose level or below when toxicity recovers to Grade ≤ 1 or baseline.

If the next cycle of treatment is delayed for > 21 days because of ATRA-related toxicities, then the patient should have study treatment discontinued unless the investigator considers that the patient will receive benefit continuing in the study. If treatment discontinuation is determined, the end of study visit should be completed within 30-40 days after the last administration of ATRA.

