All-trans retinoic acid (ATRA) has been shown in both cell lines and primary MM samples to increase CD38 expression levels and also to reduce expression of the complement-inhibitory proteins CD55 and CD59 (Nijhof et al, 2015). This resulted in significant enhancement of activity of Daratumumab in vitro and in humanized MM mouse models. Daratumumab and ATRA exhibit a strong synergy in MM cells derived from Dara-naïve patients and from patients with Dara-refractory disease, providing preclinical rationale for further evaluation of Daratumumab combined with ATRA in MM patients. Preliminary data from phase 1 trials combining Daratumumab and ATRA have shown that the combination is safe using ATRA 45 mg/m²/day dose.

Second primary malignancies will be monitored as events of interest and will be reported as a serious adverse event (SAE) regardless of causal relationship to investigational product (IP). The multicenter nature as well as the inclusion of patients in Japan of the study provides reassurance that the results are likely to have general applicability and the size of the study allows accurate description of the nature, frequency, and severity of the AE profile. Subjects will receive study treatment until PD or discontinuation. In studies evaluating agents for subjects with refractory MM or relapsed and refractory progressing or relapsed malignant diseases, it is common practice to continue study treatment until PD or intolerable toxicity develops. All subjects will be followed for OS, subsequent anti-myeloma therapies and SPMs.

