4.3. Study Duration

This study will consist of the following consecutive phases: Screening, Treatment and Follow-up.

The study will remain open to enrollment until the target subject enrollment of approximately 42 subjects has been reached. Given our current patient population we expect to complete enrollment in two years.

Each subject will be followed for up to 12 months after enrollment (unless the follow-up is shorter due to withdrawal of consent, loss to follow-up, or death).

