- ATRA should be held for AST/ALT or alkaline phosphatase ≥ 5 x ULN and/or elevation of serum total bilirubin ≥ 3 x ULN. Upon resolution of hepatotoxicity, ATRA may be resumed at a reduced dose.

Treatment repeats every 28 days for at least 8 cycles in the absence of disease progression or unacceptable toxicity. Patients achieving stable disease may continue to receive treatment in the absence of disease progression or unacceptable toxicity.

After completion of the study treatment, patients are followed up at 28 days and then every 3 months for up to 12 months. Subjects will be evaluated for disease response during each cycle and at the end of study.

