9. STATISTICAL ANALYSIS

9.1. Overview

In general, continuous data will be summarized by descriptive statistics, including number of patients, mean, standard deviation, median, minimum, and maximum. Categorical data will be summarized by the number and percentage of patients. Unless otherwise specified, data will be summarized by treatment arm. A detailed description of analysis methods will be provided in the statistical analysis plan.

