9.3. Efficacy Analysis

The primary efficacy parameter is ORR by IMWG criteria. The ORR will be evaluated using 2-sided 80% exact binomial confidence intervals. The rate variables such as CR, sCR, nCR, and VGPR will be evaluated using 2-sided 80% exact binomial confidence intervals.

The distribution of time-to-event response including DOR, TOS, PFS, and OS will be estimated by Kaplan-Meier methodology. The medians of these time-to-event efficacy responses, if available, and their 2-sided 95% CI, will be reported. In addition, the proportions of patients with events at selected time points, together with their 2-sided 95% CI will be presented. The calculations will be performed based on a fixed sample, single-stage design. Time to event analysis will be based on all data combined.

Exploratory endpoints including biomarkers, microbiome, blood variables, and exosome will be summarized descriptively.

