10.3.4. Outcome

All SAEs that have not resolved upon discontinuation of the subject's participation in the study must be followed until recovered, recovered with sequelae, not recovered (death due to another cause), or death (due to the SAE).

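### Section 7.6 withdraws patients from the study after a Grade 4 life-threatening event, which conflicts with the follow-up promised in Sections 4.2 and 4.3 and leaves PFS and OS handling undefined

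*Combined protocol and SAP*

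**What the plan says.** Section 7.6 gives the default: "For Grade 4 life threatening TEAEs, the subject will be permanently withdrawn from study". The same sentence carries an exception: "except when the investigator determines that the patient is receiving clinical benefit and there are chances to provide supportive care" against recurrence. In that case treatment may restart. Elsewhere in 7.6 the wording is different: ATRA is discontinued, or study treatment is discontinued.

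Three other places bear on follow-up:

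- Section 4.2: "All subjects will be followed for OS, subsequent anti-myeloma therapies and SPMs".
- Section 4.3: each subject is followed for up to 12 months after enrollment, "unless the follow-up is shorter due to withdrawal of consent, loss to follow-up, or death". A Grade 4 event is not among those reasons.
- Section 7.5 (and 4.1): "After completion of the study treatment, patients are followed up at 28 days and then every 3 months for up to 12 months".

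On analysis, Section 9.3 says "The distribution of time-to-event response including DOR, TOS, PFS, and OS will be estimated by Kaplan-Meier methodology"; the synopsis adds TTP. Neither defines events or censoring. Section 9.1 defers the detail: "A detailed description of analysis methods will be provided in the statistical analysis plan".

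**The concern.** Kaplan-Meier estimation assumes that a censored patient has the same later risk as those still followed. If follow-up ends because of a life-threatening toxicity, that assumption is doubtful. The exception in 7.6 adds to the doubt: it keeps patients judged to be benefiting, so those who leave would tend to be patients judged not to benefit. Departure would then depend on both toxicity and perceived efficacy, and the curves would probably be biased upward. More patients would not remove that bias, and follow-up that was not done is hard to recover later.

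The endpoints at stake are PFS, TTP, DOR and OS, all secondary and descriptive. The concern is about data collection after a patient stops, not about whether or how treatment should stop.

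**Working it through.** The plan states no PFS or OS sample size, event count or withdrawal rate, so there is no figure of its own to reproduce. The check has two parts.

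**1. The passages side by side**

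- *Survival.* Sections 4.2 and 4.3 say follow-up continues; 7.6, read literally, says it stops. The sentence in 4.2 is weaker support than it looks: its paragraph also refers to patients in Japan, while the synopsis lists two US sites, so it may be carried over from another protocol.
- *Death from the event itself.* Section 10.3.4 says: "All SAEs that have not resolved upon discontinuation of the subject's participation in the study must be followed until recovered", or until another listed outcome including death. Section 10.6 makes any death a reportable SAE, and 10.10 covers at least 30 days after the last dose. A death from the Grade 4 event should therefore be captured. A later death, after the event has resolved, is not secured this way.
- *Progression.* No sentence says that progression is assessed after withdrawal for toxicity. Sections 4.1 and 7.5 place response evaluation in each cycle and at the end of study. In Table 1, as I read it, the SPEP/UPEP/SFLC row has entries at screening and Day 1 of cycles, and none at End of Treatment or Follow-up.

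**2. Illustrative size if these patients were censored at withdrawal**

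Inputs from the documents: median PFS 8.8 and median OS 17.5 months, from the Dara + Pom + Dex study cited in Section 1 (not design assumptions of this trial), and a maximum of 42 patients. Assumed, because the documents give nothing: survival is exponential, a share q of those at risk leaves at month 2, and their hazard is then multiplied by HR. Section 9.4 stops the trial if Grade 4 events exceed 10% in any one non-hematologic organ class, but that does not cap the total.

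With λ = ln 2 / median:

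- Kaplan-Meier limit with censoring at withdrawal: exp(−λt).
- True survival: exp(−2λ) × [(1 − q) exp(−λ(t − 2)) + q exp(−HR·λ(t − 2))].

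OS at 12 months, q = 10%, HR 2: λ = 0.0396. The curve shows exp(−0.475) = 0.622. The true value is 0.924 × (0.9 × 0.673 + 0.1 × 0.453) = 0.601. The gap is 2.0 points.

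| q | HR | PFS shown / true | PFS gap | OS shown / true | OS gap |
|---|---|---|---|---|---|
| any | 1 | 0.389 / 0.389 | 0 | 0.622 / 0.622 | 0 |
| 5% | 2 | 0.389 / 0.378 | 0.011 | 0.622 / 0.612 | 0.010 |
| 10% | 2 | 0.389 / 0.367 | 0.021 | 0.622 / 0.601 | 0.020 |
| 10% | 4 | 0.389 / 0.353 | 0.035 | 0.622 / 0.578 | 0.043 |
| 20% | 2 | 0.389 / 0.346 | 0.042 | 0.622 / 0.581 | 0.041 |
| 20% | 4 | 0.389 / 0.318 | 0.070 | 0.622 / 0.535 | 0.086 |

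(12-month values; gaps taken before rounding.) Spreading withdrawal evenly over the first 6 months changes little: at HR 2, true 12-month OS is 60.3% for 10% withdrawn and 58.5% for 20%, against 62.2% shown.

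I use 12-month values because Section 4.3 follows each patient for up to 12 months after enrollment, so a 17.5-month median could not be observed under it. For scale, the approximate 95% half-width at 12 months with 42 patients and no earlier censoring is 1.96 × √(0.62 × 0.38 / 42) = 0.147, about 15 points.

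**The case against.** A reader might infer that the plan censors every Grade 4 patient from PFS and OS, and hence that the curves are too optimistic. The documents do not support that. No section says these patients are censored. Withdrawal is a default with an investigator exception, not universal. For OS, Sections 4.2 and 4.3 point the other way, and 10.3.4 should capture a death from the event. Direction and size depend on inputs found nowhere in the plan, and the bias is zero if later hazard is unchanged. All of this stands.

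It can also be said that 7.6 uses its terms loosely: a decision to discontinue treatment triggers an end of study visit, so withdrawal from study may only mean off treatment. That reading is possible, but a site can equally take the words literally, and nothing tells it not to.

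The bias shown is smaller than the sampling error, and the phase 2 decision rests on ORR. Both are true, and they limit the importance of the point.

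Finally, the gap in progression data may not come from 7.6 at all. If Table 1 schedules no disease laboratory tests after treatment, later progression is unscheduled for everyone who stops treatment. This also stands, and it means that rewording 7.6 alone would not secure PFS or TTP.

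**Conclusion.** The conflict between Section 7.6 and Sections 4.2 and 4.3 is real, and the handling of these patients in PFS, TTP, DOR and OS is undefined. If 7.6 is followed literally, the Kaplan-Meier estimates would probably be biased upward. The size is unknown. Under the assumptions above, the 12-month overstatement ranges from 0 to about 9 points for OS and 0 to about 7 points for PFS, and is about 2 points for each at 10% withdrawn and a hazard ratio of 2. A stronger statement, that the plan as written censors these patients and inflates the curves, goes beyond the text. The primary ORR decision is not affected by these curves. The point is worth correcting before patients are lost from follow-up.

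**What to change.** 1. Reconcile 7.6 with 4.2 and 4.3 so that leaving treatment is distinct from leaving the study. Confirm that the OS sentence in 4.2 is meant for this trial.
2. State that patients who stop for toxicity remain in the planned 3-monthly follow-up for survival and subsequent therapy, and are not censored at the toxicity for OS.
3. For PFS and TTP, state that progression data continue to be collected after treatment stops, and align the disease-laboratory row of Table 1 with this. Define events and censoring for all four endpoints in Section 9.3 or the SAP.
4. The Grade 4 provisions also differ among themselves. Section 7.5 has daratumumab dose delay for Grade 4 hematologic toxicity, Table 4 stops study treatment for Grade 4 rash and pomalidomide for other Grade 4 non-hematologic events, the ATRA rules below Table 8 stop ATRA, and 7.6 withdraws the patient from study. These must be reconciled; which rule applies is for the sponsor.

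The cost is a short text change plus continued data collection, including disease laboratory results at follow-up, for a few patients: 10% of 42 is about four, and 20% about eight. If Table 1 is extended for everyone who stops treatment, the laboratory cost is somewhat larger.

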3. STUDY ENDPOINTS

Primary Endpoints:

Phase 1b: The percentage of patients with treatment emergent adverse events (TEAEs) overall and per dose level.

- Patients with DLTs at each dose level.
- Patients with Grade ≥ 3 TEAEs
- Patient with serious adverse events (SAEs)
- Patients who discontinue because of TEAEs
- Patients with dose modifications (delays, interruptions, dose reductions)
- Clinically significant laboratory values

Phase 2: ORR as defined by IMWG criteria (subjects progressing on Dara + Len + Dex)

Secondary Endpoints:

- 1) ORR as defined by IMWG criteria (subjects progressing on Dara + Pom + Dex)
- 2) Rate of CR, sCR, or nCR
- 3) Rate of VGPR
- 4) TTP
- 5) DOR
- 6) PFS using Kaplan Meier
- 7) OS using Kaplan Meier

Exploratory Endpoints:

Explorative endpoints of samples collected before, during and after treatment with Dara + ATRA, + Pom + Dex and include but are not limited to the following:

- 1) Gut Microbiome analysis
- 2) Immune cell subset analyses
- 3) Analyses of cytokine, chemokine, inflammatory/anti-inflammatory and bacterial translocation markers
- 4) Basic peripheral blood laboratory variables
- 5) Genetic and epigenetic profiles

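### Sections 7.5 and 7.6 conflict on whether ATRA may restart after a life-threatening Grade 4 non-hematologic event, and neither says which prevails

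*Combined protocol and SAP*

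**What the plan says.** Section 7.5 (Dose Modification), in the bullets after the ATRA dose-reduction table, states: "ATRA will be discontinued for any Grade 4 non-hematologic toxicity". No exception or restart is attached. The next bullet, on Grade 3 toxicity, does provide for resumption.

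Section 7.6 (Criteria for Discontinuing ATRA and Discontinuation from Study) states: "For Grade 4 life threatening TEAEs, the subject will be permanently withdrawn from study". The same sentence continues "except when the investigator determines that the patient is receiving clinical benefit", with the further condition that supportive care may keep the event from recurring. For those patients, "treatment may be restarted at the previously safe dose level or below when toxicity recovers to Grade ≤ 1 or baseline".

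The phase 1b primary endpoint in Section 3 is reported as percentages of patients, overall and per dose level. Its list includes "Patients who discontinue because of TEAEs" and a separate item for patients with delays, interruptions or dose reductions.

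**The concern.** Both sections have a claim to govern. Section 7.3 sends the reader to Section 7.5 for dose modifications, while Section 7.6 is the section headed for discontinuing ATRA. An investigator could follow either in good faith, and the synopsis lists two sites.

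What is at stake is first the patient: one section ends ATRA after the event, and the other allows treatment to begin again under conditions. Second, the two phase 1b items record what was done with treatment, so a difference in management between sites passes into the counts.

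**Working it through.** There is no plan figure to reproduce. The check is a comparison of text.

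**Step 1: which events fall under both rules.** The Section 7.5 rule covers Grade 4 non-hematologic toxicity. It stands in text headed for ATRA-related toxicities, so it may be limited to events attributed to ATRA. The Section 7.6 rule covers Grade 4 TEAEs that are life threatening, hematologic or not, and says nothing on attribution. The overlap is Grade 4 non-hematologic events that are also life-threatening TEAEs, and possibly only the ATRA-related ones among them.

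**Step 2: what each rule directs for an event in the overlap.**

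| | Section 7.5 | Section 7.6, default | Section 7.6, exception |
|---|---|---|---|
| ATRA | Ends | Ends, with withdrawal | May restart, if the restart covers ATRA |
| Study participation | Not ended by this rule | Ends permanently | Continues |
| Investigator discretion | None stated | None | Yes, with conditions |

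The sections differ in both directions. The exception in 7.6 is more permissive than 7.5, because it allows a restart. The default in 7.6 is more restrictive, because it removes the patient from the study and not only from ATRA. Neither section refers to the other on this point.

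**Step 3: whether the restart in Section 7.6 includes ATRA.** The sentence speaks of treatment without naming a drug. Three features point to ATRA:
- The section heading names it.
- The section's opening sentence makes stopping ATRA after a Cycle 1 DLT depend on whether the investigator thinks retreatment could be dangerous.
- ATRA is the only drug escalated by dose level (Sections 4.1 and 7.4).

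One feature is neutral: Tables 5 and 7 also use dose levels, for reductions of pomalidomide and dexamethasone. The text favours including ATRA but does not settle it.

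**Step 4: how one event would be counted.**
- *Site follows 7.5.* ATRA stops and the other drugs may continue. The patient counts as discontinued if the item means ATRA, but not if it means all study treatment or the study. Section 3 does not say which.
- *Site follows the 7.6 default.* The patient has left the study and counts as discontinued on any meaning.
- *Site follows the 7.6 exception and restarts ATRA.* The patient counts under dose modification and not under discontinuation.

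**Step 5: what does not move.** DLTs are defined by type, grade and timing of event, or by delay of Cycle 2 (Section 7.3). The MTD is set from DLT counts (Section 7.4). The Section 9.4 stopping rules count events and deaths. ORR follows the IMWG criteria. None of these definitions uses the ATRA discontinuation rule.

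**The case against.** The best case for the plan is that the sections do different jobs. Section 7.5 would govern ATRA, and Section 7.6 would govern withdrawal from the study, with its restart meant for the other drugs or for hematologic Grade 4 events. This shows that the contradiction is less explicit than a quick reading suggests. It does not remove it, because the heading and opening of Section 7.6 concern ATRA and nothing limits the restart to other drugs. The reading is not clean for those drugs either: Table 4 discontinues pomalidomide for related Grade 4 non-hematologic events and mentions no restart.

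It is also fair to say that a restart under Section 7.6 is conditional on benefit, supportive care, recovery and a limit on dose level, and that the two phase 1b items are descriptive, with no test or threshold. A patient who stops is counted as stopped. Both points stand. They limit the consequence to what sites do and to who then enters each count.

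Three stronger readings are tempting and are not supported:
- *That every Grade 4 non-hematologic event falls under both rules.* Section 10.3 does label Grade 4 as life threatening, but in a fallback scale for events that CTCAE does not define. Section 7.6 adds life threatening as a qualifier, Section 10.6 ties that term to actual risk of death at the time, and Section 9.4 recognises asymptomatic Grade 4 laboratory abnormalities.
- *That the pseudotumor cerebri text contradicts the Grade 3 rule in Section 7.5.* One says "ATRA should be resumed at full dosage", the other "at which time it may be resumed at a reduced dose". But the first is a rule for one named event, has no stated grade, starts at half dose and reaches full dose only without worsening. A specific rule beside a general one is ordinary drafting.
- *That the size can be read from the shift caused by one patient in a small cohort.* That is only 1/n. It would apply to any single event and says nothing about this conflict.

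**Conclusion.** The concern holds in a narrow form. For Grade 4 non-hematologic events that are also life-threatening TEAEs, two sections of the same protocol give opposing directions on restarting ATRA and different directions on what ends, with no order of precedence. That is an internal contradiction, not a missing detail.

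Its size cannot be estimated, because the documents give no expected rate of such events. The effect is on re-exposure and consistent conduct at the two sites, and secondarily on two descriptive phase 1b items.

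The conclusion rests on one reading, that the restart in Section 7.6 includes ATRA. If the sponsor meant otherwise, the restart conflict would fall away. The difference between stopping ATRA and leaving the study would remain, and the protocol would still need to say what was meant. No view is taken on which clinical rule is right.

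**What to change.** - Reconcile the Grade 4 bullet in Section 7.5 with the Grade 4 text in Section 7.6 so that one rule applies, and cross-refer the sections. The clinical team must decide which rule that is.
- State in Section 7.6 whether the treatment that may restart includes ATRA, and check the result against the Grade 4 wording for pomalidomide in Table 4.
- State in Section 3, and in the matching synopsis list, whether the discontinuation item means ATRA, all study treatment or the study.

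The cost is protocol wording, by amendment. Sample size, decision rules and the analysis of response do not change.
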